4.3 Strategies for Recruitment and Retention

The MS Comprehensive Care Center of NYU Langone Medical Center has an extensive recruitment base. Patients will be recruited to participate in studies from all over New York and the other regions within the continental United States. Patients who are seen by medical staff at NYU Langone Medical Center, who fit the eligibility criteria, will be referred for the study by the study PI and sub-investigators. All physicians and medical staff at the MS Care Center will be presented with the study description.

A patient who is seeing one of these medical staff members as their treating physician will be introduced to the study by that medical staff member. If the patient is interested and agrees to be contacted by the study team, then a member of the study staff will contact them. Once a patient is identified, study staff will meet with the patient or call them to provide additional information regarding study participation. After the patient has reviewed

CONFIDENTIAL

This material is the property of the NYU School of Medicine and Langone Medical Center. Do not disclose or use except as authorized in writing by the study sponsor

Interventional Template Version: 28 APR 2017

the consent form and asked all questions, and provides consent to participate, the patient will be enrolled in the study.

Advertisements:

An IRB approved flyer will be posted in local physician offices and waiting rooms and throughout NYU, the surrounding community, and on Long Island. A description of the study will be posted on MS related websites

4.4 Duration of Study Participation

Participants will complete study activities for approximately 5 to 7 hours total over the course of 10 sessions.

> The baseline visit will last approximately 1.5-2 hours (30 minutes to consent, 60 minutes for baseline measures and 20 minutes for tDCS session 1) minutes where initial study measures are administered.

At the baseline visit, participants may be provided with a wristwatch accelerometer ActiGraph. They will be asked to wear the ActiGraph wristwatch for the entire study duration until the follow-up visit, except for during water-related events such as bathing, showering and swimming. The first tDCS and PA session will be scheduled from 4 to 7 days after the baseline visit. During this window of time (baseline to first study session), participants daily activity will be recorded through the ActiGraph wristwatch. Due to the limited availability of study actigraph devices, use of the ActiGraph will be optional and at the discretion of study staff. If the Actigraph is not being used then the first session will occur same day as baseline.

> Remote study sessions 2 through 10 will be approximately 20 minutes in duration, as follows: 20 min: tDCS (active or sham) session while performing PA program lasts 20 min (cycling paired with simultaneous tDCS)

*** Please note that while 10 sessions will be scheduled consecutively across a two-week period, the participant will be able to complete any missed sessions during the 3rd week.**

> Follow-up (Visit 11) will take approximately 1 hour to repeat baseline measures.

> A final follow-up visit will be approximately 1 hour after around four weeks from the end of the treatment. Participants will return the wristwatch accelerometer (ActiGraph) at the follow-up visit and complete gait assessment and self-reported questionnaires.

	Gait and Balance assessment and self-report questionnaires	Gait, Balance, and Functional mobility Measures	EEG with Cognitive Testing*	tDCS (active or sham) + PA	Actigraph Wristwatch Assigned*	Actigraph Baseline*	Actigraph Wristwatch Returned*
Baseline	x				x*	x*	
Session 1		x	x*	x			
Session 2		x		x			
Session 3	x			x			
Session 4	x			x			
Session 5	x			x			
Session 6	x			x			
Session 7	x			x			
Session 8	x			x			
Session 9		x	x*	x			
Session 10	x			x			
Treatment-End Visit	x		x*				x*
Follow-up (4 weeks ± 1 week post-	x*						

CONFIDENTIAL

This material is the property of the NYU School of Medicine and Langone Medical Center. Do not disclose or use except as authorized in writing by the study sponsor

Interventional Template Version: 28 APR 2017

Session 10)- Optional							
An asterisk next to a measure indicates that it is an optional assessment that may be foregone in the case of limited time and/or limited availability of the ActiGraph Wristwatch device							

4.5 Total Number of Participants and Sites

Recruitment will end when approximately N=80 participants are enrolled. A 10% potential dropout rate will leave an approximate total of N=72 evaluable participants for the study (refer to sample size estimation).

4.6 Participant Withdrawal or Termination

4.6.1 Reasons for Withdrawal or Termination

Participants are free to withdraw at any time upon request as participation is completely voluntary.

The study site's Investigator can request a withdrawal.

An investigator may terminate participation in the study if:

- Any clinical adverse event (AE), or other medical condition or situation occurs such that continued participation in the study would not be in the best interest of the participant
- The participant meets an exclusion criterion (either newly developed or not previously recognized) that precludes further study participation

Explicit subject stop criteria have been uploaded as a supporting document.

4.6.2 Handling of Participant Withdrawals or Termination

If a participant wishes to withdraw from the study they may do so at any point. The participant can be contacted by e-mail, telephone or other minimum-level contact.

4.7 Premature Termination or Suspension of Study

This study may be temporarily suspended or prematurely terminated if there is sufficient reasonable cause. Written notification, documenting the reason for study suspension or termination, will be provided by the suspending or terminating party to [name]. If the study is prematurely terminated or suspended, the PI will promptly inform the IRB and will provide the reason(s) for the termination or suspension.

Circumstances that may warrant termination or suspension include, but are not limited to:

- Demonstration of efficacy that would warrant stopping
- Insufficient compliance to protocol requirements

Study may resume once concerns about safety, protocol compliance are addressed and satisfy IRB.

4.8 Study Behavioral Intervention

To date, despite significant progress in the development of disease-modifying drugs, pharmacologic therapy alone does not warrant optimal care in pwMS. In fact, exercise has been recognized as a feasible form of self-management for people with disease [White et al, 2004]. Regular exercise can improve daily activity, cardiovascular fitness, muscle strength, health perception, and fatigue indices in pwMS [Motl et al., 2012]. For these reasons, physical activity has been used and recommended in pwMS to reduce muscle tightness, prevent joint stiffness, correct postural instability, and gait abnormalities. Cycling and walking training share similar locomotor patterns of reciprocal flexion and extensions movements and have alternating muscle activation of antagonists, and they are the most used physical exercise in rehabilitation settings.

4.8.1 Administration of Intervention

Physical activity program based on cross-trainer machine

CONFIDENTIAL

This material is the property of the NYU School of Medicine and Langone Medical Center. Do not disclose or use except as authorized in writing by the study sponsor

Interventional Template Version: 28 APR 2017

Participants will perform the aerobic exercise-conditioning program with the use of an ergonomic cross-trainer for 20 minutes while receiving concurrent tDCS. During the cycling protocol, participant will maintain a level of perceived exertion between 5 and 8 (Hard and Really Hard) on Borg Scale (Halabchi et al., 2017). The assessment of perceived exertion will make sure that participant will train safely at the correct intensity to achieve physical benefits for the PA program. Borg Scale will be administered by the study technician every 5 minutes during the 20-minutes exercise training.

4.9 Study Procedural Intervention Description

4.9.1 Administration of Procedural Intervention

Study technicians trained to oversee tDCS sessions will administer the tDCS treatments. Training includes familiarity with the device and all of its safety features. Furthermore, technicians will be trained to properly oversee the physical activity sessions to ensure a safe environment.

Procedure for the administration of the treatment:

Electrodes preparation: the $5 \times 5 \text{ cm}^2$ carbon rubber electrodes work with saline solution in order to increase conductance. Inject 5 ml of saline solution on the external surface of the carbon rubber of each electrode.

Electrodes montage: The carbon rubber sponge electrodes will be placed according to the International 10-20 EEG System. The anodal electrode will be attached at Cz position on the scalp, which corresponds to the lower limb motor cortex. The cathodal electrode will be attached at the supraorbital area on the forehead. Before starting stimulation session check the impedance. Study technicians will troubleshoot the connection if the impedance is high enough that the device cannot reliably stimulate.

Arm 1: Active tDCS and physical training

Participants will receive active tDCS while performing physical training (see detailed description in Section 6.3). A direct current of 2.5 mA will be applied throughout the stimulation session.

Arm 2: Sham tDCS and physical training

Participants will receive a sham tDCS while performing physical training (see detailed description in Section 6.3). During a sham session, the device is programmed to ramp up to the desired intensity (target 2.5 mA) and ramp down for the initial 60 seconds, with no current delivery during the session, and then again at the end of the session. These brief periods of stimulation serve to mimic the effects of a true stimulation session.

Schedule of the intervention procedure: 20 minutes of active/sham stimulation, once daily, scheduled for 10 business days over the course of approximately two weeks. The participant will be able to compensate for any missed session the week after to complete a total of 10 visits. The total duration of the treatment will be approximately 3.3 hours (20 mins x 10 sessions).

4.9.2 Remotely-Supervised tDCS Sessions

Following procedures for our validated protocol ^{25, 69}, participants will receive training on the use of the study tDCS device and preconfigured laptop computer. Participants will be given a study laptop computer which will be configured with VSee⁶⁷ and TeamViewer⁶⁸. VSee is a HIPAA compliant teleconferencing video software that encrypts data before sending, creating a secure connection between two computers. TeamViewer is a HIPAA compliant program for remote access to directly provide technical support. A tDCS kit will be provided for the participant to take home which will include the tDCS device, tDCS headset, and the one-time use sponge pockets for electrodes. The Cubii will be shipped to the participant's address.

The remotely-supervised sessions will be administered by study technicians who will be connected live with participants via the study provided laptop when initiating and delivering the treatment and can address and document any safety concerns that arise during treatment. The tDCS device is pre-programmed with a single-use unlock codes that must be entered each day in order for the stimulation to begin. The code will be provided by the study technician each day after the participant meets all safety checkpoints. Study technicians will direct headset placement remotely and will observe the patient for duration of the session in real-time. The technicians

CONFIDENTIAL

are IRB approved study team members who completed CITI, HIPAA, and study-specific training in tDCS, Vsee, and Team Viewer.

If the participant wishes to discontinue the session at any time, they will be instructed to press the "abort" key, which ramps down and ceases the stimulation current within 30 seconds and afterwards permits headset removal.

At each treatment session, participants will complete brief adverse event reports before and after treatment.

Figure 1: Example of RS-tDCS equipment and setup

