6.1 Specification of Safety Parameters

6.1.1 Definition of Adverse Events (AE)

An **adverse event** (AE) is any symptom, sign, illness or experience that develops or worsens in severity during the course of the study. Concurrent illnesses or injuries acquired during the course of the study should be regarded as adverse events. Abnormal results of diagnostic procedures are considered to be adverse events if the abnormality:

- results in study withdrawal
- is associated with a serious adverse event
- is associated with clinical signs or symptoms
- leads to additional treatment or to further diagnostic tests
- is considered by the investigator to be of clinical significance

CONFIDENTIAL

This material is the property of the NYU School of Medicine and Langone Medical Center. Do not disclose or use except as authorized in writing by the study sponsor

Interventional Template Version: 28 APR 2017

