6.2.2 Relationship to Study Agent

The clinician's assessment of an AE's relationship to study agent (device) is part of the documentation process, but it is not a factor in determining what is or is not reported in the study. If there is any doubt as to whether a clinical observation is an AE, the event should be reported. All AEs must have their relationship to study agent

CONFIDENTIAL

This material is the property of the NYU School of Medicine and Langone Medical Center. Do not disclose or use except as authorized in writing by the study sponsor

Interventional Template Version: 28 APR 2017

assessed. In a clinical trial, the study product must always be suspect. To help assess, the following guidelines are used.

- **Related** – The AE is known to occur with the study agent, there is a reasonable possibility that the study agent caused the AE, or there is a temporal relationship between the study agent and event. Reasonable possibility means that there is evidence to suggest a causal relationship between the study agent and the AE.
- **Not Related** – There is not a reasonable possibility that the administration of the study agent caused the event, there is no temporal relationship between the study agent and event onset, or an alternate etiology has been established.

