6.3 Time Period and Frequency for Event Assessment and Follow-Up

The occurrence of an AE or SAE may come to the attention of study personnel during study visits and interviews of a study participant presenting for medical care. All AEs including local and systemic reactions not meeting the criteria for SAEs will be captured on the appropriate RF. Information to be collected includes event description, time of onset, Co-I's assessment of severity, relationship to study product (assessed only by those with the training and authority to make a diagnosis), and time of resolution/stabilization of the event. All AEs occurring while on study must be documented appropriately regardless of relationship. All AEs will be followed to adequate resolution.

Any medical condition that is present at the time that the participant is screened will be considered as baseline and not reported as an AE. However, if the study participant's condition deteriorates at any time during the study, it will be recorded as an AE. UPs will be recorded in the data collection system throughout the study.

Changes in the severity of an AE will be documented to allow an assessment of the duration of the event at each level of severity to be performed. AEs characterized as intermittent require documentation of onset and duration of each episode.

The PI will record all reportable events with start dates occurring any time after informed consent is obtained until 7 (for non-serious AEs) or 30 days (for SAEs) after the last day of study participation. At each study visit, the investigator will inquire about the occurrence of AE/SAEs since the last visit. Events will be followed for outcome information until resolution or stabilization.

All unresolved adverse events should be followed by the investigator until the events are resolved, the subject is lost to follow-up, or the adverse event is otherwise explained. At the last scheduled visit, the investigator should instruct each subject to report any subsequent event(s) that the subject, or the subject's personal physician, believes might reasonably be related to participation in this study.

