7.2.4 Safety Analyses

Safety will be assessed through the number of adverse events that occur over the course of the study. Adverse event rates will be compared to that of published literature.

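### The pre-session adverse event report has no role in the safety analysis, so symptoms arising after screening but before a session are pooled with events during stimulation

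*Combined protocol and SAP*

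**What the plan says.** All references are to the combined protocol and SAP.

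- **Collection.** Section 4.9.2: "At each treatment session, participants will complete brief adverse event reports before and after treatment". Section 3.4.2 also takes pain ratings on both sides of each session and asks participants to rate AEs.
- **Objective.** The AE and pain row of the section 15 table concerns what happens during stimulation. Section 5.3.3 likewise records and rates events for each stimulation session.
- **Definition.** Section 6.1.1 defines an AE as "any symptom, sign, illness or experience that develops or worsens in severity during the course of the study".
- **Baseline.** Section 6.3 excludes a medical condition "present at the time that the participant is screened will be considered as baseline and not reported as an AE", unless it deteriorates. It requires all other on-study AEs to be documented whatever their cause, with time of onset, severity and relationship.
- **Relationship.** Section 6.2.2 classes each AE as related or not related. One of the routes to related is that "there is a temporal relationship between the study agent and event".
- **Analysis.** Section 7.2.4 is two sentences: "Safety will be assessed through the number of adverse events that occur over the course of the study", and "Adverse event rates will be compared to that of published literature".
- **Use of the rates.** Under 6.4.1, AE rates go to the safety review meetings, and rates above those in the literature lead the investigator to put the study on hold. Sections 6 and 6.6 place these reviews after every ten completers.

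**The concern.** The paired reports are what is needed to tell a symptom that appears or worsens with a session from one that was already there. No section says how the pre-session report enters any count. The only baseline is screening, and the only planned summary is the study-wide number of AEs.

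Take a headache that is absent at screening and present on the pre-session form of session 5. It developed during the study, so it is an AE under 6.1.1 and enters the 7.2.4 count. Nothing in the analysis separates it from a headache that began during the session.

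Two things are at stake. The tolerability figure answers a wider question than the stated objective. And the comparison with published rates, both in the final analysis and in the reviews that can lead to a hold, partly reflects symptoms of MS and daily life.

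**Working it through.** **Step 1: set the sections side by side.**

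| Question | What the plan says | Section |
|---|---|---|
| When are AEs reported? | Before and after each session | 4.9.2 |
| What is the objective? | Events and pain during stimulation | 15 (also 5.3.3) |
| What is the baseline? | Screening | 6.3 |
| What is counted? | All AEs over the study | 7.2.4 |
| Role of the pre-session report? | None stated | – |
| Restriction to related events or by onset time? | None stated | 7.2.4 |
| Comparator? | Published rates | 7.2.4, 6.4.1 |

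This is how symptoms of different origin are treated:

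- Present at screening and not worse: excluded (6.1.1, 6.3).
- Arising after screening and present before a session: counted.
- New or worse during a session: counted.

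The second and third groups are pooled. That follows from the text and needs no figure.

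**Step 2: illustrate the size.** The plan gives no figure here to reproduce.

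Inputs from the documents: 10 sessions per participant (4.9.1), 80 participants (4.5), and a published headache rate e = 14.8% (2.4.1). Section 2.4.1 does not say whether that rate is per participant, per session or per study. I read it as per participant, which is an assumption.

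Assumed input: b, the chance that an unrelated headache is present before a given session. It is not in the documents. I use 0.5% to 10%, and take b as independent of the stimulation effect.

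- Expected pre-session reports = 80 × 10 × b. For b = 1%, 2%, 5% and 10% this is 8, 16, 40 and 80.
- If sessions are independent, the chance of at least one is 1 − (1 − b)^10, and the apparent participant rate is 1 − (1 − e)(1 − b)^10.
- If the same participants carry the symptom at every session (complete dependence), the chance of at least one is b, and the apparent rate is 1 − (1 − e)(1 − b).

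| b | At least one, independent | Apparent rate, independent | Apparent rate, complete dependence |
|---|---|---|---|
| 0.5% | 4.9% | 19.0% | 15.2% |
| 1% | 9.6% | 22.9% | 15.7% |
| 2% | 18.3% | 30.4% | 16.5% |
| 5% | 40.1% | 49.0% | 19.1% |
| 10% | 65.1% | 70.3% | 23.3% |

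Worked case for b = 1%. Independent: 1 − 0.852 × 0.99^10 = 1 − 0.852 × 0.9044 = 22.9%. Complete dependence: 1 − 0.852 × 0.99 = 15.7%.

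In this illustration, counting only events new or worse than the same session's pre-session report returns 14.8%.

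**The case against.** The strongest reply is that counting every on-study AE is correct. Section 6.1.1 defines AEs that way, 6.3 requires documentation whatever the cause, and a headache that is new before session 5 is properly an AE. Onset time, severity and relationship are also recorded, so the separation can be made later. All of this stands. What remains is that 7.2.4 neither uses these items nor states a measure that matches the objective.

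A second reply is that from session 2 the pre-session report follows earlier stimulation. A symptom on it may be a delayed or carry-over effect, and a measure that subtracts it would lose that. This also stands, and it is why the new summary must be added to the all-AE count and not replace it.

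A third is that the published rates may themselves include background symptoms. The documents do not say. If they do, the all-AE count is the closer match, which is a reason to show both figures.

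A reader might also infer more than the text supports:

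- *That every symptom present before stimulation is counted as an AE.* It is not. Symptoms present at screening and not worse are excluded.
- *That such symptoms will be called related.* The temporal route in 6.2.2 permits this but does not compel it. The same section provides for not related where another cause is established, and 7.2.4 does not restrict the count by relationship in any case.
- *That background symptoms cost power in an active versus sham comparison of AEs.* Section 7.2.4 plans no such test, so there is no power to lose, and the documents give no arm-specific risks from which to compute it.

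**Conclusion.** The point holds as a gap in the analysis. The plan collects a same-day pre-session report, states an objective about events during stimulation, and then specifies only a study-wide count in which the report has no role. Symptoms arising between screening and a session are pooled with session events in the literature comparison and in the rate review under 6.4.1. This conclusion rests on the text alone.

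The size is unknown. The inflation figures depend on the assumed background rate, on the correlation between sessions within a person, and on reading 14.8% as a per-participant rate. At b = 1% the apparent headache rate lies between 15.7% and 22.9%. Recurrent symptoms are likely to cluster within people, so the independent figures are better read as the high end. Section 6 describes the common side effects as confined to the electrode site on the scalp, so general MS tingling is not an obvious match for the published tingling rate. The figures do not show that the trial's rates will exceed the published ones.

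This is a worthwhile, low-cost improvement to a secondary safety outcome. It is not a flaw in the AE definition or in AE reporting.

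**What to change.** In 7.2.4, keep the all-AE count under 6.1.1 and add a session-emergent AE summary beside it:

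- **Definition:** an event that is new, or rated more severe, on the post-session report than on the same session's pre-session report.
- **Presentation:** by arm, as the number and percentage of participants with at least one such event and of sessions with one.
- **Use:** show both figures wherever rates are set against the literature, including at the periodic safety reviews, and say which published rates are used and in what unit. This leaves the hold provision in 6.4.1 as it is.

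The cost is a few sentences of analysis text and one derived variable. Both reports are already collected. The one thing to confirm is that the pre- and post-session forms carry the same symptom list and the same severity rating, since 4.9.2 does not describe their content.

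The limitation to state in the plan is that delayed and carry-over effects appear only in the all-AE table, so the two tables must be read together.
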